## 10.11 Site Heterogeneity

Site poolability will be evaluated using a random effects meta-analysis approach using the R package *metafor* to implement the analysis. True effects are assumed to be normally distributed with mean  $\mu$  and variance  $\sigma^2$ .

By imposing a specified distribution on the site-to-site variability, i.e. a normal distribution with mean  $m$  and variance  $t^2$ , sensitivity to small sample sizes in individual sites is reduced and the parameters reflecting the magnitude of site-to-site variability are naturally derived. The quantitative measure of the magnitude of heterogeneity is  $I^2$ .  $I^2$  is the fraction of  $t^2$  that is due to effect size heterogeneity, as opposed to sampling variance. Fractions 25% and less are considered small. If there is significant site to site variability, the impact on this variability will be evaluated using a Bayesian hierarchical model estimated using *WinBUGS*.

This will be done by translating hypotheses of interest to the log odds ratio scale and using MCMC to determine the Bayesian posterior probabilities of the described results. Poolability according to baseline demographic and disease severity status will be evaluated in descriptive stratified analyses.

## 11 Risks

The potential risks for subjects enrolled in the trial include those related to surgery, lumbar spine surgery, interspinous spacers (including the X-STOP® IPD®, Superior® ISS and other interspinous spacers) and instrumentation, the Superior® ISS, or radiographs for the study that are not standard of care. There is always a chance that unforeseen risks may occur.

**Risks generally associated with any surgery include:**

- anesthetic medication reactions
- surgery at the incorrect location, side or level
- blood loss, blood vessel damage, phlebitis or hematoma
- blood transfusion which may cause circulatory collapse, blood incompatibility, kidney damage, hepatitis, infection with HIV
- myocardial infarction or circulatory problems
- deep vein thrombosis, pulmonary embolism or thrombus formation in other vessels
- stroke
- fever or infection
- pneumonia
- injury to muscle, soft tissues or nerves
- wound swelling, draining or delayed healing
- discomfort and rehabilitation associated with recovery from surgery
- inability to perform certain tasks, such as lifting, exercising etc.
- death

**Risks associated with lumbar spine surgery include:**

- damage to nerve roots or the spinal cord causing partial or complete sensory or motor loss (paralysis)
- loss of bladder and/or bowel functions
- dural leaks (tears in the tissue surrounding and protecting the spinal cord)
- instruments used during surgery may break or malfunction which may cause damage to the operative site or adjacent structures
- fracture, damage or remodeling of adjacent anatomy, including bony structures or soft tissues during or after surgery
- new or worsened back or leg pain

**Risks associated with lumbar spine implants (including the X-STOP® IPD®, Superior® ISS and other interspinous spacers) and associated instruments include:**

- sensitivity or allergy to the implant material
- failure of the device/procedure to improve symptoms and/or function
- pain and discomfort associated with the operative site or presence of implants
- implant malposition or incorrect orientation
- spinous process fracture
- wear debris which may damage surrounding soft tissues including muscle or nerve
- scar tissue may form at implant site
- migration or dislodgement of the implant from the original position so that it becomes ineffective or causes damage to adjacent bony or soft tissues including nerve
- implant may loosen, fatigue, deform, break or disassemble which may require another operation to remove the implant and may require another method of treatment
- re-operation to remove or replace the implant

**Risks specifically associated with the Superior® ISS include:**

- implant may deform, break or disassemble; specifically the cam lobes may collapse or fail to lock
- other unexpected reactions may also occur

**Risks Associated with Radiographs of the Lumbar Spine**

The series of radiographs required for this study are similar to the standard of care for patients with Lumbar Spinal Stenosis treated with traditional surgical procedures such as laminectomy with or without spinal fusion. The risk of any side effects from this low level of exposure is very small. A 4-view X-ray of the lumbar spine (AP, lateral, flexion, extension) will be obtained at baseline, and at 6 weeks, 3, 6, 12, 18 and 24 month follow-up visits with a 2-view at the immediate post-operative time point. It is estimated that the total millirems will be less than 200 millirems per visit (for a 4 view x-ray) or no more than 1300 millirems for this study. This exposure can be compared to the allowable annual radiation dose for nuclear medicine/radiation oncology workers of 1800 millirems per year.

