### 6.5.4 Post-Procedure Visits

***The following was collected at the Discharge Assessment for treated patients (0-7 days)***

Most patients were discharged the day of procedure. If clinically indicated, some patients stayed for up to 23 hours or were admitted based on co-morbid conditions.

Discharge Assessment: 

• Visual Analogue Scale (VAS) to assess leg and back pain

• Medical treatment

• Adverse event

• Concomitant medication and treatment

• Length of hospital stay

• Type of anesthesia

Neurological Assessment: 

• Muscle strength

• Sensory and Reflexes

• Range of motion

• Palpation of pulses

• Straight leg raise

• Femoral Stretch

Radiographic studies: 

• Standing Anterior/Posterior Lumbar Spine X-ray

• Lateral Lumbar Spine X-ray

***The following information was/will be collected at the Follow-up Visits for treated patients at 6-week ( $\pm 2$  weeks), 3-month ( $\pm 2$  weeks), 6-month ( $\pm 1$  month), 12-month ( $\pm 2$  months), 18-month ( $\pm 2$  months), 24-month ( $\pm 2$  months), and will be collected annually ( $\pm 3$  months) thereafter through 60 months as required by this protocol:***

Subject Self-Report Questionnaires: 

• Zurich Claudication Questionnaire (ZCQ)

• Visual Analogue Scale (VAS)

• SF-12 version 2 Health Related Quality of Life

• Oswestry Disability Index (ODI)

• VertiFlex Patient Satisfaction Questionnaire

Neurological Assessment: 

• Muscle strength

• Sensory and Reflexes

• Range of motion

• Palpation of pulses

• Straight leg raise

• Femoral Stretch

Follow-up Assessment: 

• Work status and time to return to work or normal ADL (activities of daily living)

• Leg and back pain

• Medical treatment

• Adverse event

• Concomitant medication and treatment, including narcotic usage

Radiographic studies :

- Standing Anterior/Posterior Lumbar Spine X-ray
- Lateral Lumbar Spine X-ray
- Flexion/Extension Lateral Lumbar Spine X-rays

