### **Bibliography**

Appendix A: Visit Schedule												
	Screening -Baseline	Surgical Treatment	Discharge (±0-7 days)	6-week (±2 weeks)	3-month (±2 weeks)	6-month (±1 month)	12-month (±2 months)	18-month (±2 months)	24-month c (±2 months)	36-month c (±2 months)	48-month c (±2 months)	60-month c (±2 months)
Study Visit Window		Day 0	0-7 days	4-8 wks	10-14 wks	5-7 mos	10-14 mos	16-20 mos	22-26 mos	22-26 mos	22-26 mos	22-26 mos
Signed Informed Consent	X											
Demographic Information	X											
Complete History & Physical	X											
Randomization	X											
Standing AP & Lateral Lumbar Spine X-rays	X a		X	X	X	X	X	X	X	X	X	X
Flexion / Extension Lateral Lumbar Spine X-rays	X a			X	X	X	X	X	X	X	X	X
Lumbar Spine MRI/CT Scan	X a											
DEXA Scan b	As needed											
SF-12 –Health Survey (v2)	X			X	X	X	X	X	X	X	X	X
Zurich Claudication Questionnaire (ZCQ)	X			X	X	X	X	X	X	X	X	X
Oswestry Disability Index (v2)	X			X	X	X	X	X	X	X	X	X
Neurological Status	X		X	X	X	X	X	X	X	X	X	X
Visual Analogue Scale	X		X	X	X	X	X	X	X	X	X	X
VertiFlex ® Patient Satisfaction Questionnaire				X	X	X	X	X	X	X	X	X
Assess Adverse Events		X	X	X	X	X	X	X	X	X	X	X

aLumbar spine x-rays and MRI/CT taken within 3 months of enrollment can be used to confirm eligibility.

bIn order to confirm eligibility, at the Investigator’s discretion, subjects previously diagnosed with osteoporosis, osteopenia, osteomalacia, female subjects over the age of 65, and post-menopausal female subjects under the age of 65 with any of the risk factors for osteoporosis, will have DEXA scans performed prior to study entry.

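### Section 11 gives a 1300 millirem maximum for radiographs on a schedule that stops at Month 24, so it is not a supported maximum for a protocol that requires films through Month 60

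*Combined protocol and SAP*

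**What the plan says.** In Section 11, under the heading on radiographs of the lumbar spine, four views are specified (AP, lateral, flexion, extension); the series "will be obtained at baseline, and at 6 weeks, 3, 6, 12, 18 and 24 month follow-up visits". One further set of two views is taken straight after the operation. The paragraph estimates "less than 200 millirems per visit (for a 4 view x-ray") and a total of "no more than 1300 millirems for this study". It sets that total beside an allowable annual dose of 1800 millirems for radiation workers. No visit after Month 24 appears in it.

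Section 6.5.4 lists AP, lateral and flexion/extension films among the assessments at every follow-up visit, and continues those visits annually "thereafter through 60 months as required by this protocol". Appendix A agrees: the rows "Standing AP & Lateral Lumbar Spine X-rays" and "Flexion / Extension Lateral Lumbar Spine X-rays" are both marked in the 36-, 48- and 60-month columns. Section 5.2.2 uses a 60-month radiograph for the maintenance-of-distraction endpoint.

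**The concern.** This protocol exists to carry follow-up from 24 to 60 months. The films missing from the radiation paragraph are those of the period it adds. The paragraph looks like text kept from the 24-month study. The Protocol Summary shows a similar trace: it still defines maintenance of distraction at 24 months, where Section 5.2.2 says 60.

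The opening of Section 11 names study radiographs as a source of risk, and this paragraph is the only place where that risk is given a number. Section 13.1 requires initial and at least annual IRB approval. An IRB relying on the protocol would read a maximum that the protocol's own visit schedule does not support.

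**Working it through.** **Inputs**

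- Four-view visit: under 200 millirems (Section 11). I use 200 as the ceiling.
- Two-view post-operative film: no dose is given. I assume half a four-view series, 100 millirems, and then vary it from 0 to 200.
- Four-view follow-ups listed in Section 11: six (6 weeks; 3, 6, 12, 18 and 24 months). Baseline is also listed.
- Further four-view visits in Section 6.5.4 and Appendix A: three (Months 36, 48 and 60).

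**Step 1: reproduce the stated figure.** Bound = (number of four-view visits x 200) + two-view dose.

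- Six follow-ups plus the two-view film: 6 x 200 + 100 = 1300. This matches exactly.
- Combinations that do not match at the ceiling: follow-ups only, 6 x 200 = 1200; baseline added without the two-view film, 7 x 200 = 1400; baseline and two-view film both included, 7 x 200 + 100 = 1500.

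**Step 2: extend to Month 60 on the same basis.**

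- Added series: 3 x 200 = 600.
- New bound: 9 x 200 + 100 = 1900.
- Shortfall: 1900 - 1300 = 600, and 600 / 1300 = 46%.

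**Step 3: vary the assumed two-view dose and the treatment of baseline.**

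| Two-view dose | Bound to Month 60, baseline not counted | Bound to Month 60, baseline counted |
|---|---|---|
| 0 | 9 x 200 = 1800 | 10 x 200 = 2000 |
| 100 | 1900 | 2100 |
| 200 | 2000 | 2200 |

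Every entry is above 1300.

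**Step 4: what would make 1300 hold through Month 60?** With the two-view film at half a four-view dose, nine series plus one half-series is 9.5 units, and 1300 / 9.5 = about 137 millirems per four-view visit. With baseline it is 1300 / 10.5 = about 124. The documents give no average that low; they give only the ceiling of 200.

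**Step 5: does 1300 leave out baseline?** With baseline, the Month 24 schedule is 7.5 units, and 1300 / 7.5 = about 173 millirems per four-view visit. That is compatible with a dose under 200. The exact match in Step 1 makes the reading without baseline plausible but does not prove it.

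**The case against.** The 200 figure is a strict ceiling and the two-view dose is assumed, so 1900 is a bound on exposure and not an estimate of it. Actual exposure could stay under 1300. This stands, and it limits the conclusion to what the protocol can support as a maximum.

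A reader might infer that 1300 also omits the baseline series listed in the same sentence, and so that the true bound is 2100, or 62% above the stated one. The documents do not establish this. Step 5 shows that 1300 can include baseline through Month 24. If baseline was left out, there may be a reason: the opening of Section 11 confines radiograph risk to films beyond standard of care, and a footnote to Appendix A lets films taken within three months of enrollment serve for eligibility. The protocol simply does not say whether baseline is counted.

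A reader might also infer that the corrected total breaches the 1800 millirem limit. It does not show that. The 1800 is per year, and the study total builds up over about five years. On the same assumptions, the heaviest year by scheduled visits (baseline, discharge, 6 weeks, and 3, 6 and 12 months) is 5 x 200 + 100 = 1100, and the three omitted visits fall one to a year at no more than 200 each.

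It could be argued that the 1300 refers to something other than the full follow-up. If it meant the extension alone, the bound would be 600 and 1300 would be safe. That reading fails, because the paragraph lists baseline to Month 24 and none of the extension visits.

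Finally, this is leftover wording in a risk section. It touches no endpoint or analysis, and sites are told the right visits in Section 6.5.4 and Appendix A. That is true and keeps the matter modest, but it does not make the stated maximum correct.

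**Conclusion.** The point holds as an internal contradiction with a numerical consequence. The 1300 millirem maximum rests on a visit list ending at Month 24, while the protocol requires three more four-view series. On the basis that reproduces 1300, the supported bound through Month 60 is 1900. The 600 millirem increment depends only on the 200 ceiling and three added visits; the exact total also depends on the assumed two-view dose and on whether baseline counts. Under every combination examined the bound exceeds 1300.

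It is not shown that every patient, or any given patient, receives more than 1300. Nor can it be said that patients were given a wrong figure: the consent pages are not among the documents available, so what they state is unknown. The primary analysis is unaffected.

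**What to change.** Reconcile the radiograph paragraph in Section 11 with Section 6.5.4 and Appendix A:

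- list every x-ray visit the protocol requires through Month 60;
- state whether the baseline series is counted and, if not, why;
- give the dose used for the two-view film, and recompute the total from the per-visit figures;
- put the comparison with 1800 millirems on the same time basis, either a yearly study dose against the annual figure or a cumulative dose against a cumulative one;
- check whether the risk information given to IRBs and patients carries the 1300 figure and, if so, replace it.

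The cost is wording in one paragraph and in any matching risk information, and a less favourable stated maximum. No change to the x-ray schedule is proposed.

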**Fluoroscopy Exposure**

Fluoroscopy was used intra-operatively to ensure correct placement of the Superior® ISS device, and the X-STOP® IPD® device, between the spinous processes. Doses are similar to those used during fusion surgery or to administer non-operative treatments such as epidural injections, facet blocks or nerve root blocks. Sources of morbidity associated with the use of fluoroscopic guidance include, but are not limited to: early transient erythema, main erythema reaction, temporary epilation, permanent epilation, and dermal necrosis. These are usually associated with longer radiation exposures and higher doses than expected during the study surgery.

**12 Benefit Analysis**

The clinical benefits of the Superior® ISS have been documented through clinical study under IDE No. G070118, and may include the relief of symptoms associated with LSS. The potential benefit for subjects who are enrolled in the clinical investigation and receive the FDA-approved X-STOP® IPD® may include the relief of symptoms associated with LSS. An additional potential benefit for subjects who are enrolled in the clinical investigation and who receive the Superior® ISS is the possibility of less patient morbidity and tissue trauma, since the device can be percutaneously inserted through a 15 mm incision compared to the 4 cm (40 mm) incision needed to implant the X-STOP® IPD® device.

Although subjects enrolled in the clinical investigation may receive no direct benefit from participating, the knowledge gained from this investigation may benefit both physicians treating patients and patients who have LSS by generating data regarding the safety and outcome of the treatments.

## **13 Investigator Responsibilities**

### **13.1 IRB Approval**

This study must have initial and continuing approval (at least annual) from an Institutional Review Board (IRB) responsible for approving clinical studies. This can be a local or central IRB.

Screening or enrollment of subjects into the trial did not commence until the IRB approval letter was received by the Sponsor. In addition, a copy of the IRB approval letter must be filed on-site in the Investigator's study binder. Where appropriate, amendments to the protocol will be submitted for IRB review and approval before implementation.

### **13.2 Protocol Adherence**

The Investigator(s) agree to conduct the study in accordance with this protocol. Prior to beginning the study, the Investigator(s) must sign the *Investigator Agreement* and the *Protocol Signature Page* of this protocol.

An Investigator must not make any changes in the study without first receiving approval in writing from the Sponsor and IRB, except when necessary to eliminate apparent immediate hazards to a subject.

### **13.3 Review of Source Documents**

The Investigator(s) agrees that the Sponsor's employees or designees, as well as FDA designees will have the right to audit and review pertinent medical records relating to this clinical trial.

### **13.4 Record of Device Inventory**

The Investigator(s) will maintain a Device Accountability Log of all investigational devices received, used, or returned during this study. The Device Accountability Log should be available during monitoring visits. All investigational devices not used in this study must be returned to the Sponsor before or at the completion of the study or at the Sponsors request.

### **13.5 Data Recording and Record Retention**

1. All data will be recorded on Case Report Forms for each subject enrolled in the study as well as in the subject records (source documentation).
2. The Sponsor or Sponsor's designee will review completed Case Report Forms, along with source documentation. The Investigator(s) will ensure that the medical records are made available for review by the study monitor or FDA, as required.
3. All subject study records are to be maintained in a secure storage facility until notified by the Sponsor that the records may be discarded. This includes the following documentation:

- i) Case Report Forms, Informed Consents and enrollment logs
- ii) Device Accountability Logs and device shipment receipts of all devices shipped to the site
- iii) Correspondence with the IRB, Sponsor, FDA, Monitor, or other Investigators
- iv) Study protocol and any amendments issued
- v) Protocol and Informed Consent approvals from the IRB
- vi) Clinical Study Agreement and curricula vitae of Investigator(s), and the site personnel signature form

### **13.6 Notification Reporting**

The Investigator(s) is responsible for all reporting required per the IRB.

## **14 Sponsor Obligations**

### **14.1 Investigator(s) Training**

Prior to the first procedure, the Sponsor provided appropriate training to each Investigator that included didactic and hands on elements, e.g., cadaver lab, sawbones, model. Training addressed topics including surgical procedures, selection of appropriate implant sizes, instrumentation for implantation, indications for use of the device, contraindications and management of complications. The Sponsor also provided appropriate training to the operating room staff at each investigational site. Investigators were trained on use of the control device. Each site was permitted to enroll up to 2 non-randomized patients to receive the Superior® ISS as training cases prior to randomizing the first patient.

### **14.2 Sponsor Study Termination**

The Sponsor may close enrollment or terminate the study at any site, at any time, for any of the reasons listed below. If a site was closed to enrollment or terminated before enrolling randomized patients, the site could be replaced in the study. Patients identified as training cases that receive implants will be followed until they reach their 60 month follow-up or the study is terminated.

- 1. Non-compliance to GCP guidelines or protocol
- 2. Failure to enroll subjects in a timely manner
- 3. Protocol deviations
- 4. Inaccurate or incomplete data
- 5. Unsafe or unethical practices
- 6. Safety or efficacy considerations
- 7. Administrative decision

### **14.3 Study Monitoring and Frequency of Monitoring Visits**

Study monitoring will be carried out in compliance with FDA regulations (21CFR 812) and all GCP guidelines. The clinical investigation will be monitored throughout its active phase, i.e., until 60 month follow-up is complete for all subjects. The first Monitoring Visit occurred shortly after the first subject was enrolled and treated at the site. Subsequent Monitoring Visits will occur as the frequency of follow-up dictates, but no less than annually.

#### Periodic Monitoring Visit Activities

1. The Monitor's visit to the clinical site will include review of:
  - a. Subject Source Documentation
  - b. Case Report Forms
  - c. Informed Consents
  - d. Protocol Adherence
  - e. Investigational Device Accountability
2. Reports:
  - a. The Monitor should complete a report documenting completion of each Periodic Monitoring visit.
3. Site Close-out Activities
  - a. When the study has been completed or terminated, the Monitor will assure that all site Close-out activities have been completed.
  - b. The Monitor should complete a report documenting completion of site Close-out Monitoring visit.

### **15 Informed Consent**

A copy of the proposed Informed Consent document should be submitted to Sponsor for review and approval before submission to the IRB. Study enrollment may not have begun until Sponsor reviewed the document and it was approved by the IRB.

All subjects enrolling in the study:

- a. Were informed of the investigational nature of the study
- b. Were given the opportunity to ask any questions regarding the study treatment
- c. Voluntarily and willingly signed the Informed Consent prior to study treatment
- d. Were given a copy of the Informed Consent

## **List of Appendices**

### **Appendix A: Visit Schedule**

### **Appendix B: Patient Questionnaires**

Zurich Claudication Questionnaire

Oswestry Disability Index

Visual Analog Scale

SF-12

VertiFlex® Patient Satisfaction Survey

### **Bibliography**

Appendix A: Visit Schedule												
	Screening -Baseline	Surgical Treatment	Discharge (±0-7 days)	6-week (±2 weeks)	3-month (±2 weeks)	6-month (±1 month)	12-month (±2 months)	18-month (±2 months)	24-month c (±2 months)	36-month c (±2 months)	48-month c (±2 months)	60-month c (±2 months)
Study Visit Window		Day 0	0-7 days	4-8 wks	10-14 wks	5-7 mos	10-14 mos	16-20 mos	22-26 mos	22-26 mos	22-26 mos	22-26 mos
Signed Informed Consent	X											
Demographic Information	X											
Complete History & Physical	X											
Randomization	X											
Standing AP & Lateral Lumbar Spine X-rays	X a		X	X	X	X	X	X	X	X	X	X
Flexion / Extension Lateral Lumbar Spine X-rays	X a			X	X	X	X	X	X	X	X	X
Lumbar Spine MRI/CT Scan	X a											
DEXA Scan b	As needed											
SF-12 –Health Survey (v2)	X			X	X	X	X	X	X	X	X	X
Zurich Claudication Questionnaire (ZCQ)	X			X	X	X	X	X	X	X	X	X
Oswestry Disability Index (v2)	X			X	X	X	X	X	X	X	X	X
Neurological Status	X		X	X	X	X	X	X	X	X	X	X
Visual Analogue Scale	X		X	X	X	X	X	X	X	X	X	X
VertiFlex ® Patient Satisfaction Questionnaire				X	X	X	X	X	X	X	X	X
Assess Adverse Events		X	X	X	X	X	X	X	X	X	X	X

aLumbar spine x-rays and MRI/CT taken within 3 months of enrollment can be used to confirm eligibility.

bIn order to confirm eligibility, at the Investigator’s discretion, subjects previously diagnosed with osteoporosis, osteopenia, osteomalacia, female subjects over the age of 65, and post-menopausal female subjects under the age of 65 with any of the risk factors for osteoporosis, will have DEXA scans performed prior to study entry.

